### **6.3. Preparation/Handling/Storage/Accountability**

Please refer to the 208887 MP.

### **6.4. Measures to Minimize Bias: Randomization and Blinding**

Please refer to the 208887 MP.

### **6.5. Concomitant Therapy**

Please refer to the 208887 MP.

### **6.6. Dose Modification**

Dose modification is for belantamab mafodotin when in combination with dostarlimab. For information related to overall dose modification refer to the 208887 MP. Also see 208887 MP Section 11 for guidelines on dose modification and management of events for belantamab mafodotin and other partner combination treatments.

**Table 10      Permitted Dose Reductions for Belantamab Mafodotin when in Combination with Dostarlimab**

Belantamab mafodotin) Starting Dose Level	1st Dose Reduction
2.5 mg/kg	1.9 mg/kg
1.9 mg/kg	

- If the participant cannot tolerate belantamab mafodotin after the allowed dose reductions, he or she must be withdrawn from study treatment for lack of tolerability.
- Resuming treatment with belantamab mafodotin may be considered after the toxicity has resolved to Grade 1 or less.
- For further details regarding dose modifications see 208887 MP Section 11.

No dose reductions are allowed for dostarlimab.

Dose Modification Guidelines for immune related Adverse Events are listed in the 208887 MP Section 11. For immune related encephalitis event of any Grade, dostarlimab should be discontinued.

If belantamab mafodotin is held or discontinued for any toxicity, dostarlimab is also to be held or discontinued.

## **7. DISCONTINUATION OF STUDY INTERVENTION AND PARTICIPANT WITHDRAWAL FROM THE STUDY**

Please refer to the 208887 MP.

### **7.1. Discontinuation of Study Intervention**

Please refer to the 208887 MP.

### **7.2. Participant Withdrawal from the Study**

Please refer to the 208887 MP.

### **7.3. Lost to Follow Up**

Please refer to the 208887 MP.

## **8. STUDY ASSESSMENTS AND PROCEDURES**

Please refer to the 208887 MP for the overall Study Assessments and Procedures for the study.

Information and details specific to Sub-study 4 are in Section [8.3.7](#), Section [8.3.10](#) and Section [8.4](#) below.

### **8.1. Efficacy Assessments**

Please refer to the 208887 MP.

### **8.2. Safety Assessments**

Planned time points for all safety assessments are provided in the SoA tables (Section [1.3](#)).

### **8.3. Adverse Events and Serious Adverse Events**

#### **8.3.1. Time Period and Frequency for Collecting AE and SAE Information**

Please refer to the 208887 MP.

#### **8.3.2. Method of recording AE and SAE information**

Please refer to the 208887 MP.

#### **8.3.3. Method of Detecting AEs and SAEs**

Please refer to the 208887 MP.

### **8.3.4. Follow-up of AEs and SAEs**

Please refer to the 208887 MP.

### **8.3.5. Reporting of Potentially Life-Threatening AEs to the GSK Medical Director**

Please refer to the 208887 MP.

### **8.3.6. Regulatory Reporting Requirements for SAEs**

Please refer to the 208887 MP.

### **8.3.7. Management of Pregnancy**

Details of all pregnancies in female participants will be collected after the start of study treatment and for 4 months following last dose of belantamab mafodotin.

Details of all pregnancies for female partners of male participants will be collected after the start of study treatment and 6 months following last dose of belantamab mafodotin.

### **8.3.8. Cardiovascular and Death Events**

Please refer to the 208887 MP.

### **8.3.9. Disease-Related Events and/or Disease-Related Outcomes Not Qualifying as SAEs**

Please refer to the 208887 MP.

### **8.3.10. Adverse Events of Special Interest**

Information on belantamab mafodotin AESI are contained in the 208887 MP Section 8.3.10.

Immune-related TEAEs for dostarlimab are summarized in Section 5.4.6 of Dostarlimab IB v5 [[Dostarlimab](#), 2021].

## **8.4. Treatment of Overdose**

Guidelines for management of belantamab mafodotin overdose are contained in the 208887 MP Section 8.4.

An overdose of dostarlimab is defined as any dose that is  $\geq 20\%$  than the intended dostarlimab dose. For fixed doses, an overdose of dostarlimab is defined as any dose that is  $\geq 20\%$  than 1000 mg Q6W. All overdoses, regardless of associated AE/SAE are to be reported as described for SAEs and as per the SAE form completion guidelines. Obtain an additional plasma sample for PK analysis if requested by the GSK Medical Director.

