**Table 1 Location of Sub-study 4-specific Content**

Section	Heading title	Brief description of content
1.3	Schedules of Activities	Comprehensive SoA tables specific for Sub-study 4
2.1	Rationale for Combination of Belantamab mafodotin with Dostarlimab (GSK4057190)	Explanation why treatment with belantamab mafodotin and dostarlimab is expected to be complementary
2.2	Background for Dostarlimab (GSK4057190)	Available data on clinical pharmacology, safety and clinical activity
2.3	Benefit/Risk Assessment	Risk assessments for dostarlimab treatment; benefit assessment summary
4.1	Overall Design	Description of dose escalation design for the combination treatment
4.3	Justification for Dose	Data for the basis of the planned dostarlimab dosing
5.2	Exclusion Criteria	Three additional exclusion criteria were defined for Sub-study 4
6.1	Study Intervention(s) Administered	Specifications for belantamab mafodotin and dostarlimab IP
6.2	Administration of Belantamab mafodotin and Dostarlimab	Specifications for administration of belantamab mafodotin and dostarlimab
6.6	Dose Modification	Detailed directions guidance for dose modifications of combination treatment
8.3.7	Management of Pregnancy	Timeframes for on data collection
8.3.10	Adverse Events of Special Interest	Information on dostarlimab AESI
8.4	Treatment of Overdose	Guidance for potential drug overdose for dostarlimab
8.8	Biomarkers	Summary of the biomarker research being conducted for sub-study 4
12.13	Appendix 13: Protocol Amendment History	Summary of Changes Tables for Sub-study 4 specific amendments

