#### **Dostarlimab Monotherapy Study 4010-01-001**

Study 4010-01-001 is an ongoing, first-in-human Phase 1 study of dostarlimab to evaluate the safety and tolerability, PK, pharmacodynamics, and clinical activity of dostarlimab in participants with recurrent or advanced solid tumors.

A total of 21 participants were dosed in the dose escalation phase of the study (Part 1). Dose escalation continued to a maximally administered dose of 10 mg/kg every 2 weeks (Q2W) and a maximum tolerated dose was not identified. No dose limiting toxicities (DLTs) were observed. The PK of dostarlimab were dose proportional across the dose range tested. Receptor occupancy was measured by direct binding of dostarlimab to PD-

1 on T cells from participants in Part 1 and by the dostarlimab induced inhibition of IL-2 production after ex vivo stimulation of T cells from participants in Part 1. Maximal receptor occupancy was achieved at all doses tested (1, 3, and 10 mg/kg) down to dostarlimab plasma concentrations as low as 2.435 µg/mL and was maintained for approximately 29 days.

The pharmacokinetic/pharmacodynamic (PK/PD) data was used to determine the fixed dosing tested in Part 2A of the study. In this phase of the study, the safety and tolerability of dostarlimab were evaluated at 2 fixed dosing schedules: 500 mg every 3 weeks (Q3W) and 1,000 mg every 6 weeks (Q6W). The recommended therapeutic dose (RTD) regimen was determined to be 500 mg Q3W for 4 cycles followed by 1,000 mg Q6W for all cycles thereafter.

The RTD selection was based on a combination of results from a preliminary 2-compartment population PK model, receptor occupancy data from peripheral blood cells of participants in Part 1, and safety data from Part 2A, wherein the 500 mg Q3W and 1,000 mg Q6W regimens were found to have acceptable tolerability with no observed DLTs. In Part 2A, the PK and pharmacodynamic data confirmed that both dosing regimens provided sufficient and sustained drug concentrations to allow for maximal receptor occupancy throughout the dosing cycle.

The RTD is being evaluated in expansion cohorts for mismatch repair-deficient (dMMR)/microsatellite instability high (MSI H) and MMR proficient/microsatellite stable (MSS) endometrial cancer, non small cell lung cancer (NSCLC), and dMMR/MSI H and/or polymerase  $\epsilon$ -mutated non endometrial cancer in Part 2B of study. The PK/PD profile of participants in Part 2B of the study was similar to that of participants in Part 2A of the study.

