#### **4.1. Overall Design**

Overall design is in relation to the dose exploration of combination treatment belantamab mafodotin co-administered with dostarlimab being described in this Sub-study.

The starting dose of belantamab mafodotin will be 1.9 mg/kg to be evaluated in Dose Level 1, with the highest dose of belantamab mafodotin of 2.5 mg/kg planned for Dose Level 2.

The dose of dostarlimab will be identical across the dose level groups and will be 500 mg Q3W for 4 cycles followed by 1000 mg Q6W for subsequent cycles.

Please see 208887 MP Section 4.1.1 for details of decision making during the DE phase.

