### **Dostarlimab**

- Participants will receive dostarlimab starting C1D1 and will be treated until disease progression, intolerable toxicity, informed consent withdrawal, the end of the sub-study, study or death. There is no pre-specified duration of therapy after which administration must be stopped.
- Dostarlimab will be administered using IV infusion on Day 1 of each treatment cycle after all procedures and assessments have been completed.
- Dostarlimab will be administered at flat prescribed dose (outlined below) over 30 min IV infusion time after at least 1 hour rest period after completion of belantamab mafodotin infusion. Premedication is not required prior to infusion unless deemed medically necessary, in which case it should be administered according to institutional guidelines/recommendations.
  - 500 mg every 3 weeks for the first 4 doses, followed by
  - 1000 mg every 6 weeks.
- Visit window for treatment of dostarlimab allowed by the protocol is  $\pm$  3 days for both Q3W and Q6W schedule. However, it is recommended that sites try to keep participants on the original dosing schedule based on C1D1 and maintain the dosing intervals as closely as possible to the Q3W and Q6W schedule, respectively. If in the judgment of the Investigator, belantamab mafodotin and dostarlimab combination treatment needs to be initiated prior to the next planned scheduled dose *following a dosing delay and where clinical toxicity has resolved*, please discuss with the Medical Director.
- In case of IRR during or after preceding belantamab mafodotin infusion, the administration of dostarlimab will be delayed to allow for recovery to Grade 1 or less. In total, the infusion of dostarlimab may be delayed for up to the allowed +3-day window from the scheduled dose date to allow for recovery, and to accommodate scheduling conflicts in a given cycle. If the participant does not recover from IRR to Grade 1 or less within the +3 day window, the dosing of dostarlimab will be skipped in a given cycle, and may be resumed in the next cycle.

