1.3. Study Design

Overview of Study Design and Key Features				
Please refer to the 208887 Master SAP for overall Study Design for the study.				
Design Features	
 Refer to the 208887 Master SAP for the key design features for the study 			
Study intervention	
 The Starting Dose (SD) for belantamab mafodotin in study 208887 will be 1.9 mg/kg Q3W in combination with other anti-cancer treatments but may vary by sub-study. Dostarlimab is to be given at least one hour following completion of belantamab mafodotin infusion. 			
Dose Level	Belantamab Mafodotin mg/kg IV Q 3 weeks	Dostarlimab mg IV Q 3 weeks	Dostarlimab mg IV Q 6 weeks	
1	1.9 mg/kg	500 mg, cycles 1 – 4	1000 mg, cycle 5 and every odd cycle thereafter	
2	2.5 mg/kg	500 mg, cycles 1 – 4	1000 mg, cycle 5 and every odd cycle thereafter	
	
 Dostarlimab will be administered as a 30-minute IV infusion at the prescribed flat dosing 			
Time & Events	
 Refer to Section 1.3: Schedule of Activities (SoA) in Sub-study 4 modular protocol 			
Treatment Assignment	
 In DE phase, treatments will be assigned to participants with predefined algorithm. 			
Interim Analysis	
 The Interim Analysis (IA) planned in the DE will not be carried out. 			
Blinding	
 This is an open label study. In DE phase, participants will be assigned to available treatment slots by a predetermined algorithmic approach. 			

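### Protocol 8.4 defines a dostarlimab overdose against two reference doses without saying which governs, so at the 500 mg visits the threshold is either 600 mg or 1200 mg

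*Protocol*

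**What the plan says.** Protocol Section 8.4 gives two definitions in consecutive sentences. The first sets the limit at 20% or more "than the intended dostarlimab dose". The second reads "For fixed doses, an overdose of dostarlimab is defined as any dose that is" 20% or more than the 1000 mg six-weekly dose. Both omit the comparative word, which I take to be *greater*. Nothing says whether the second sentence adds to the first, narrows it or replaces it. The consequence is explicit: "All overdoses, regardless of associated AE/SAE are to be reported as described for SAEs".

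The dosing provisions are:

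- Protocol 6.2 gives dostarlimab as a flat dose, "500 mg every 3 weeks for the first 4 doses, followed by" 1000 mg every six weeks. Protocol 4.1 and SAP 1.3 agree; SAP 1.3 has "1000 mg, cycle 5 and every odd cycle thereafter".
- Protocol 6.6 permits no dostarlimab dose reductions.
- Protocol 2.2.1, describing the monotherapy study, says dostarlimab was "evaluated at 2 fixed dosing schedules: 500 mg every 3 weeks (Q3W) and 1,000 mg every 6 weeks (Q6W".

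Table 1 of the protocol describes the content of Section 8.4 as "Guidance for potential drug overdose for dostarlimab". Section 8.4 sends the reader to the Master Protocol for belantamab mafodotin overdose only.

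**The concern.** Every dostarlimab dose in this sub-study is flat, and the protocol elsewhere counts 500 mg Q3W as fixed dosing. The fixed-dose sentence as written therefore reaches doses 1 to 4, where the intended dose is 500 mg and its reference dose of 1000 mg is twice that. A site that takes the specific sentence as overriding the general one would not class a doubled 500 mg dose as an overdose. A site that follows the first sentence would.

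What is at stake is the reporting of overdoses, which Section 8.4 requires even when no adverse event follows. An asymptomatic doubled dose would not be picked up through adverse event collection (Protocol Tables 3 and 5). Deviation tracking (SAP 6.1.3) might record it, but that is not reporting by the SAE route.

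**Working it through.** The protocol states no threshold in mg, so there is no printed figure to reproduce.

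**Inputs**

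- Margin: at least 20% above the reference dose (Protocol 8.4, with *greater* supplied).
- Reference dose: the intended dose (sentence 1) or 1000 mg (sentence 2).
- Intended dose: 500 mg for doses 1 to 4, 1000 mg from dose 5 (Protocol 6.2).
- Vial content: 500 mg (Protocol 6.1).
- Participants enrolled: 4 (SAP 5).

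**Thresholds** (1.2 × reference dose)

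| Intended dose | Sentence 1 | Sentence 2 |
|---|---|---|
| 500 mg | 1.2 × 500 = 600 mg | 1.2 × 1000 = 1200 mg |
| 1000 mg | 1.2 × 1000 = 1200 mg | 1.2 × 1000 = 1200 mg |

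Relative to an intended 500 mg, the limits are 600/500 = 120% and 1200/500 = 240%. At 1000 mg they coincide.

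**Ways of combining the sentences at a 500 mg visit**

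1. Meeting either sentence is enough: the lower limit applies, 600 mg.
2. Sentence 2 is confined to the 1000 mg Q6W doses: 600 mg.
3. Sentence 2 replaces sentence 1 for fixed doses: 1200 mg.

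Under readings 1 and 2, sentence 2 adds nothing. It never lowers the limit at 500 mg, and at 1000 mg it repeats sentence 1. Under reading 3, sentence 1 has no effect, because no dose in the sub-study is other than flat. Each reading leaves one sentence idle, so redundancy alone does not settle which was meant.

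**Classification of a dose given when 500 mg is intended**

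| Dose given | % of intended | Limit 600 mg | Limit 1200 mg |
|---|---|---|---|
| 550 mg | 110% | no | no |
| 600 mg | 120% | overdose | no |
| 1000 mg (one extra vial) | 200% | overdose | no |
| 1200 mg | 240% | overdose | overdose |
| 1500 mg (two extra vials) | 300% | overdose | overdose |

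The readings disagree from 600 mg up to, but not including, 1200 mg. One extra vial is the only whole-vial error in that range. Giving the dose-5 amount too early produces the same 1000 mg.

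**Reach**: at most 4 participants × 4 doses = 16 administrations at an intended 500 mg.

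**The case against.** The strongest reply is that the sentences can be reconciled. Sentence 1 is unconditional and sentence 2 has no word such as *instead* or *only*, so nothing withdraws sentence 1. Sentence 2 also names the six-weekly schedule and can be read as limited to it. Either way the limit at 500 mg is 600 mg. The 1200 mg reading voids sentence 1 and lets a doubled dose pass. It is also fair to say that the fixed-schedule wording in Protocol 2.2.1 concerns another study, while Section 6.2 here says flat.

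That reconciliation is available, and I think 600 mg is the sensible answer. It does not close the point. Section 8.4 states no precedence, and taking a specific sentence to displace a general one is ordinary reading practice. A trigger for SAE-route reporting should not depend on which convention the site adopts.

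The practical objections carry more weight:

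- Overdose is not an endpoint (SAP 1.2), and Protocol 4.3 reports no excessive toxicity at 1000 mg Q6W in solid tumours.
- The closure decision dates from October 2021 (SAP 1.1) and the amendment from 21 January 2022. Without delays, dose 4 falls 3 × 3 = 9 weeks after dose 1, so a participant starting on 31 October 2021 would have reached it by about 2 January 2022. Individual dates are not given, and delays are possible.

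These limit the consequence but do not remove the inconsistency. The Master Protocol's SAE procedures and the Pharmacy Manual might settle practice. However, Table 1 and Section 8.4 place the dostarlimab definition in this document.

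**Conclusion.** The inconsistency is real and minor. At the 500 mg visits the protocol supports a limit of 600 mg or of 1200 mg, and the most plausible whole-vial error, one extra vial, falls between them. At 1000 mg there is no difference.

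The conclusion rests on two readings: that the missing comparative is *greater*, and that flat and fixed dosing mean the same here. The 16 administrations are a ceiling on exposure, not a count of errors. The effect is confined to overdose reporting. SAP 4.1.2 marks the 1000 mg Q6W level as not used, which suggests that the 500 mg visits are the ones that mattered in practice.

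**What to change.** Replace both definitional sentences in Protocol 8.4 with one:

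> A dostarlimab overdose is any single dose at least 20% greater than the dose intended for that administration: 600 mg or more when 500 mg is intended, 1200 mg or more when 1000 mg is intended.

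This also supplies the missing comparative. Since enrolment is closed, a clarification note would serve as well as an amendment. The cost is one sentence, with no change to data collection or to any analysis. It gives one rule for any remaining overdose review and keeps the present wording from being reused.

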**8.5. Pharmacokinetics**

Not applicable.

**8.6. Genetics**

Please refer to the 208887 MP.

**8.7. Immunogenicity Assesments**

Please refer to the 208887 MP.

**8.8. Biomarkers**

Not applicable

**8.9. Health-Related Quality of Life**

Please refer to the 208887 MP.

**9. STATISTICAL CONSIDERATIONS**

Please refer to the 208887 MP for the overall Statistical Considerations for the study.

**9.1. Statistical Hypotheses**

Please refer to the 208887 MP.

**9.2. Sample Size Determination**

Please refer to the 208887 MP.

**9.3. Populations for Analyses**

Please refer to the 208887 MP.

**9.4. Statistical Analyses**

Please refer to the 208887 MP.

**9.5. Interim Analysis**

Please refer to the 208887 MP.

**9.6. Sample Size Sensitivity**

Please refer to the 208887 MP.

## 11. GUIDELINES FOR DOSE MODIFICATION AND OTHER PARTNER COMBINATION TREATMENTS FOR ALL SUBSTUDIES

Please refer to the 208887 MP for the overall Guidelines for Dose Modification for the study.

Additional guidelines specific to Sub-study 4 are provided in [Table 11](#).

**Table 11 Guidelines for Treatment and Management of Immune-Related Adverse Events of Interest- Dostarlimab**

Toxicity	Grade/description of toxicity	Recommendations
Immune-related Encephalitis	Any grade	Permanently discontinue

**12. APPENDICES: SUPPORTING DOCUMENTATION AND  
OPERATIONAL CONSIDERATIONS****12.1. Appendix 1: Regulatory, Ethical, and Study Oversight  
Considerations**

Please refer to the 208887 MP.

**12.2. Appendix 2: Clinical Laboratory Tests**

Please refer to the 208887 MP.

**12.3. Appendix 3: AEs: Definitions and Procedures for Recording, Evaluating, Follow-up, and Reporting**

Please refer to the 208887 MP.

**12.4. Appendix 4: ECOG Performance Status**

Please refer to the 208887 MP.

**12.5. Appendix 5: NYHA Functional Classification System**

Please refer to the 208887 MP.

**12.6. Appendix 6: Modified Diet in Renal Disease**

Please refer to the 208887 MP.

**12.7. Appendix 7: Contraceptive Guidance and Collection of  
Pregnancy Information**

Please refer to the 208887 MP.

**12.8. Appendix 8: Genetics**

Please refer to the 208887 MP.

**12.9. Appendix 9: Liver Safety: Required Actions and Follow-up Assessments and Study Treatment Rechallenge Guidelines**

Please refer to the 208887 MP.

**12.10. Appendix 10: Eye Care Specialist- Qualifications and Requirements**

Please refer to the 208887 MP.

**12.11. Appendix 11: Decentralized and Remote Assessment Approaches**

Please refer to the 208887 MP.

## 12.12. Appendix 12: Abbreviations and Trademarks

ABC	Airway breathing and circulation
ADC	Antibody drug conjugate
ADCC	Antibody dependent cellular cytotoxicity
AE	Adverse event
AESI	Adverse events of Special Interest
ALP	Alkaline phosphatase
ALT	Alanine aminotransferase
APRIL	A proliferation-inducing ligand
AST	Aspartate aminotransferase
AUC	Area under the concentration-time curve
AUC (0-∞)	Area under the concentration-time curve to infinity
AUC (0-τ)	Area under the concentration time curve over the dosing interval
AV	Atrioventricular
BAFF/BlyS	B-cell activating factor/B-lymphocyte stimulator
BAL	Bronchoaveolar lavage
BCMA	B cell maturation antigen
BCRP	Breast cancer resistant protein
BCVA	Best corrected visual acuity
BED	Biologically Effective Dose
BIW	Twice a week
BLRM	Bayesian logistic regression modelling
BM	Bone Marrow
BSA	Body surface area
BWT	Body weight
CA	Competent Authority
Car-T	Chimeric Antigen T cell therapy
CBC	Complete blood count
CBR	Clinical benefit rate
CDISC	Clinical Data Interchange Standards Consortium
CE	Cohort Expansion phase
CI	Confidence interval
CK	Creatine kinase
CK-MB	Creatine kinase MB-isoenzyme
CL	Clearance
CLL	Chronic lymphocytic leukemia
Cmax	Maximum plasma drug concentration
CMMC	Circulating multiple myeloma cells
CNS	Central nervous system
CONSORT	Consolidated Standards of Reporting Trials
CPMS	Clinical Pharmacology Modeling and Simulation
CPR	Cardio-pulmonary resuscitation
CR	Complete response
CRM	Continual Reassessment Method
CRP	C-reactive protein

CRT	Calreticulin
CT	Computer tomography
CTCAE	Common Toxicity Criteria for Adverse Events
cTn	Cardiac troponin
Ctrough	Trough plasma concentration
CYP	Cytochrome P450
CV%	Coefficient of variation percent
Cys-mcMMAF	cys Monomethyl auristatin F
DAMP	Damage-Associated Molecular Pattern
DC	Dendritic cells
DE	Dose Exploration phase
DIC	Disseminated intravascular coagulation
DoR	Duration of response
DLBCL	Diffuse large B-cell lymphoma
DLT	Dose limiting toxicity
DMPK	Drug metabolism and pharmacokinetics
DNA	Deoxyribonucleic acid
EC	Ethics committee
EC50	Concentration associated with 50% maximal effect
ECG	Electrocardiogram
ECHO	Echocardiogram
ECL	Electrochemiluminescence
ECOG	Eastern Cooperative Oncology Group
eCRF	Electronic case report form
eGFR	Estimated Glomerular Filtration Rate
EM	Extramedullary
EOI	End of infusion
EORTC QLQ	European Organisation for Research and Treatment of Cancer Quality of Life Questionnaires
FACTS	Fixed and adapted clinical trials simulator
FISH	Fluorescence in situ hybridization
FLC	Free light chain
FSH	Follicle stimulating hormone
FTIH	First time in human
G-CSF	Granulocyte colony stimulating factor
GFR	Glomerular filtration rate
GI	Gastrointestinal
GLDH	Glutamate dehydrogenase
GLP	Good laboratory practice
GM-CSF	Granulocyte macrophage colony stimulating factor
GSI	Gamma secretase inhibitor
GSK	GlaxoSmithKline
GSK2857914	GlaxoSmithKline anti-BCMA antibody (CA8 J6M0 Potelligent)
GSK2857916	GlaxoSmithKline anti-BCMA antibody drug conjugate (CA8 J6M0 Potelligent MMAF)
HBs-Ag	Hepatitis B surface antigen

HBc	Hepatitis B core
HbcAb	Hepatitis B core antibody
HBV	Hepatitis B
HCV	Hepatitis C
HIPAA	Health Insurance Portability and Accountability Act
HMGB1	High mobility group box 1
HNSTD	Highest non-severely toxic dose
HPLC	High performance liquid chromatography
HRT	Hormone replacement therapy
HSCT	Hematopoietic stem cell transplant
IB	Investigator's Brochure
IC50	Concentration associated with 50% inhibition of maximal effect
ICD	Immunogenic cell death
ICF	Informed consent form
ICH	International Council on Harmonization
IDS	Integrated Data Standards Library
IEC	Institutional ethics committee
Ig	Immunoglobulin
IHC	Immunohistochemistry
IMIDs	Immunomodulators
IMWG	International Myeloma Working Group
INR	International normalized ratio
IP	Intraperitoneal
IRB	Institutional review board
IRC	Independent review committee
IRR	Infusion-related reaction
ITT	Intent-to-treat
IUD	Intrauterine device
IUS	Intrauterine hormone-releasing system
IV	Intravenous
IVRS	Integrated voice response system
KIM-1	Kidney injury molecule-1
LBCL	Large B-cell lymphoma
LDH	Lactate dehydrogenase
LFT	Liver function test
LLN	Lower limit of normal
LVEF	Left ventricular ejection fraction
MABEL	Minimum anticipated biological effect level
mAb	Monoclonal antibody
Mc	Maleimidocaproyl
MDRD	Modified diet in renal disease
MedDRA	Medical Dictionary for Regulatory Activities
MI	Myocardial infarction
MM	Multiple Myeloma
mm 	Millimeter cube
MMAF	Monomethyl auristatin F

MoA	Mechanism of action
MP	Master Protocol
MR	Minimal response
MRD	Minimal residual disease
MRI	Magnetic resonance Imaging
MSDS	Material safety data sheet
MTD	Maximum Tolerated Dose
mTNBC	Metastatic triple negative breast cancer
mTPI	Modified toxicity probability interval
MUGA	Multiple gated acquisition
NAG	N-Acetyl- $\beta$ -D-glucosaminidase
NCI-CTCAE	National Cancer Institute – Common Toxicity Criteria for Adverse Events
N-CRM	A modification of the Continual Reassessment Method (CRM) proposed by Neuenschwander et al.
NHV	Normal healthy volunteers
NICD	NOTCH intracellular domain
NF- $\kappa$ B	Nuclear factor kappa light-chain enhancer of activated B cells
NT-proBNP	N-terminal B-type natriuretic peptide
NK	Natural killer
NONMEM	Non linear mixed effects modelling
NYHA	New York Heart Association
OAT	Organic anion transporter
OATP	Organic anion transporter polypeptide
ORR	Overall response rate
OS	Overall survival
OSDI	Ocular Surface Disease Index
PBMC	Peripheral blood mononuclear cells
PCR	Polymerase chain reaction
PD	Progressive disease
PD-L1	Programmed death-ligand 1
PET	Positron emission tomography
PFS	Progression-free survival
PFT	Pulmonary function test
Pgp	P-glycoprotein
PI	Proteasome inhibitor
PK	Pharmacokinetic(s)
PK/PD	Pharmacokinetic(s)/Pharmacodynamic(s)
PR	Partial response
PRO	Patient reported outcome
PT	Prothrombin time
PTS	Platform technologies and sciences
PTT	Partial thromboplastin time
Q3W	Every 3 week
QID	4 times a day
QoL	Quality of life

RAP	Reporting and analysis plan
RAMOS	Registration and medication ordering system
REML	Restricted maximum likelihood
RIBA	Recombinant immunoblot assay
RNA	Ribonucleic acid
Ro	Observed accumulation ratio
RO	Receptor occupancy
RPA-1	Renal papillary antigen-1
RP2D	Recommended Phase 2 dose
RRMM	Relapsed/refractory multiple myeloma
RT-qPCR	Reverse transcription quantitative polymerase chain reation
RTD	Recommended therapeutic dose
SAE	Serious adverse event
sBCMA	Soluble B-cell maturation antigen
sCR	Stringent complete response
SD	Stable disease
SoA	Schedule of Activities
SoC	Standard of care
SOI	Start of infusion
SPEP	Serum protein electrophoresis
SRM	Study reference manual
SRT	Safety Review Team
SPR	Surface plasmon resonance
t½	Half-life
TALL	T-cell acute lymphoblastic leukemia
TBNK	T-cell, B-cell and Natural Killer cells
TEAE	Treatment emergent adverse event
T last	Time of last quantifiable concentration
TLS	Tumor lysis syndrome
T max	Time to maximum drug concentration
TNBC	Triple negative breast cancer
TPP	Time to progression
TTR	Time to response
ULN	Upper limit of normal
UPEP	Urine protein electrophoresis
VGPR	Very good partial response
V d	Volume of distribution
V ss	Volume of distribution at steady state
WM	Waldenstrom's macroglobulinemia
WOCBP	Women of childbearing potential

